### **1.6. Overview of Ruxolitinib**

#### **1.6.1. Clinical Safety Summary**

##### **1.6.1.1. Healthy Subject Studies**

Ruxolitinib has been administered in Novartis or Incyte sponsored clinical studies to approximately 385 healthy volunteers as single, repeat single, or multiple doses for up to 10 days' duration, 32 subjects with various degrees of renal impairment, and 24 subjects with various degrees of hepatic impairment. In healthy volunteer studies, a transient, reversible decrease in neutrophil count has been seen after doses of 25 to 50 mg, which reverses 12 to 24 hours after stopping drug. These neutropenia events were generally of Grade 1 or Grade 2 severity, with a single instance of severe Grade 4 neutropenia that led to study drug

discontinuation in 1 subject receiving 50 mg ruxolitinib twice daily (BID; highest dose). The MTD in healthy volunteers was determined to be 25 mg BID or 100 mg QD.

In a thorough cardiac QT study, it was shown that increasing plasma concentrations of ruxolitinib are not associated with increases in the QT interval.

For a review of ruxolitinib clinical safety, refer to the [ruxolitinib IB](#).

#### **1.6.1.2. Phase 3 Studies in Subjects With Myelofibrosis**

Up to 22 FEB 2018, ruxolitinib has been administered to more than 8738 subjects in Novartis- and Incyte-sponsored interventional clinical trials. Two pivotal Phase 3 studies (COMFORT-I and COMFORT-II) enrolled subjects with MF, and together they support the efficacy and safety of ruxolitinib for the treatment of patients with PMF, PPV-MF, or PET- MF. COMFORT-I, conducted in the United States, Canada, and Australia, was a double-blind, placebo-controlled study that enrolled 309 subjects, and COMFORT-II was an open-label study conducted in Europe that compared ruxolitinib with best available therapy in 219 patients.

In the randomized period of the 2 pivotal studies in MF, COMFORT-I and COMFORT-II (cutoff: 01 MAR 2011, median duration of exposure = 10.8 months) discontinuation due to AEs, regardless of causality, was observed in 11.3% of subjects. The most frequently reported adverse drug reactions were thrombocytopenia and anemia. Hematologic adverse reactions (any CTCAE grade) included anemia (82.4%), thrombocytopenia (69.8%) and neutropenia (16.6%). Anemia, thrombocytopenia, and neutropenia are dose-related effects. The 3 most frequent nonhematologic adverse reactions were bruising (21.6%), dizziness (15.3%), and headache (14.0%). The 3 most frequent nonhematologic laboratory abnormalities were raised ALT (27.2%), raised AST (18.6%), and hypercholesterolemia (16.9%).

Long-term treatment and follow-up in subjects with MF (including 615 subjects treated with ruxolitinib during the controlled and extension phases of studies INCB 18424-251: cutoff, 01 OCT 2012; COMFORT-I: 15 OCT 2015; COMFORT-II: 20 APR 2015) has shown that as expected, the numbers and proportions of AEs and SAEs has increased. However, no new safety signals have emerged (median duration of exposure for this population is 28.78 months, with 1578.45 patient-years of exposure).

#### **1.6.1.3. Other Ongoing Studies**

For a thorough discussion of the clinical safety of ruxolitinib, refer to the [ruxolitinib IB](#).

### **1.7. Justification of Study Treatment Regimen**

In clinical studies to date, DLTs have not been observed at doses of INCB050465 up to 20 mg, and target inhibition as assessed by phosphorylated protein kinase B levels in peripheral blood showed > 80% inhibition at trough in subjects receiving 5 mg, 10 mg, 15 mg, or 20 mg of INCB050465. Exploration of doses of 5, 10, 20, or 30 mg in the present study is therefore clinically reasonable. Indeed, doses of 10 or 20 mg given daily for 8 weeks followed by weekly have been well tolerated, and no DLTs were observed.

Previously, Part 3 was implemented to explore daily doses beyond Week 8. The 8-week higher dose was retained, and subjects in Part 3 either switched to weekly dosing or remained on daily doses but at a lower dose. Part 4 will use all daily dose regimens and will directly examine the

role a higher initial dose might play in overall response and duration of response. From the subject's perspective, taking the same dose every day from start to finish would be the simplest regimen to follow. However, the initial use of a higher dose might be critical to achieve significant decreases in spleen size and/or symptom scores more quickly in this refractory population. Part 4 of the study will compare a group of subjects who begin receiving INCB050465 at 20 mg QD, then decrease to 5 mg QD after 8 weeks (dose group TG5I/M) with a group who begin at and remain on doses of 5 mg QD (dose group TG5D).

All parts of the study require that subjects be on a stable dose of ruxolitinib for at least 8 weeks before the screening visit; doses of ruxolitinib may not exceed 25 mg BID for subjects with platelet counts  $\geq 100 \times 10^9/L$  and may not exceed 10 mg BID for subjects with platelet count  $\geq 50 \times 10^9/L$  but  $< 100 \times 10^9/L$ , which mirrors the recommendations for treatment doses in the ruxolitinib complete prescribing information. The requirement for a stable dose before study entry further implies adequate tolerability for the dose of ruxolitinib in a given subject.

## **1.8. Potential Risks and Benefits of the Treatment Regimen**

### **1.8.1. Potential Risks of INCB050465 Based on Preclinical Safety**

Potential risks with administration of INCB050465 based on preclinical findings include lymphoid depletion (refer to the [INCB050465 IB](#)). This may result in infections, fever, or cytokine release resulting in fever, chills, hypotension, wheezing, and/or rash.

In both rats and dogs, immunosuppression (evident as minimal to marked depletion of lymphoid tissues, including thymus, lymph nodes, spleen, and gut-associated lymphoid tissue) was observed at all doses and considered to be consistent with the pharmacologic activity of INCB050465. The incidence and severity of these findings increased with dose.

### **1.8.2. Potential Risks of INCB050465 Based on Prior Clinical Studies**

INCB050465 has effects on the immune system. Therefore, subjects must be monitored closely for evidence of infections or new cancers, and administration should be discontinued if there is evidence of clinically significant infection or new cancer.

For studies combining INCB050465 with a JAK inhibitor (eg, INCB039110, INCB052793, or ruxolitinib), all immune-related AEs must be completely resolved to baseline for 2 weeks before starting study medications, and subjects with history of Grade 3 or 4 immune-related AEs from prior immunotherapy will be excluded. Subjects with a history of immune-related ocular AEs will also be excluded.

One case of PJP has been reported with the use of INCB050465 in combination with pembrolizumab. The subject had not received PJP prophylaxis before the event. All subjects who receive INCB050465 (as monotherapy or combination therapy) will also receive PJP prophylaxis. Subjects allergic to or at risk for standard PJP prophylaxis with sulfonamide antibiotics will receive either inhaled pentamidine or atovaquone (Mepron®) for prophylaxis; dapsone should not be used in such subjects. Prophylaxis should be given while subjects are receiving study treatment and continued for 2 to 6 months after the last dose of study drug.

### 1.8.3. Potential Benefits of INCB050465 Based on Prior and Ongoing Clinical Studies

Based on emerging efficacy and safety data from the ongoing Study INCB 50465-101 (see Section 1.5.4.1), the treatment regimen for Study INCB 50465-201 Part 1 was selected to be 10 mg QD (Cohort 1) or 20 mg QD (Cohort 2) given for 8 weeks, followed by 10 mg (Cohort 1) or 20 mg (Cohort 2) given once weekly. Doses of 10 mg or 20 mg QD provide trough concentrations exceeding the IC90 (based on an *in vitro* whole-blood assay). Furthermore, 20 mg QD has demonstrated efficacy in DLBCL and in other types of NHLs. However, 24% of all subjects in study INCB 50465-101 discontinued study treatment due to an AE. Consequently, after administration of daily INCB050465 for 8 weeks in the present study, the dosing regimen was reduced to once-weekly dosing for Part 1 and Part 2.

Pharmacodynamic data from INCB 50465-101 showed that a single dose of 20 mg exhibited maximal inhibition of AKT in an *ex vivo* pharmacodynamic assay, and PK modeling suggests that 20 mg once weekly will 1) achieve maximal inhibition equivalent to approximately  $10 \times$  IC90, 2) exceed the IC90 for approximately 36 hours, and 3) have minimal to no inhibition for approximately half the dosing interval. This once-weekly regimen is similar to that of another PI3K inhibitor (copanlisib), which is administered IV on Days 1, 8, and 15 of a 28-day cycle, and which achieved 7 objective responses in 9 subjects with NHL ([Patnaik et al 2016](#)). Among the 51 subjects who received study drug, 4 discontinued treatment due to an AE. There were 2 events of Grade 3 noninfectious pneumonitis, 1 event of Grade 3 diarrhea, and no events of colitis.

This once-weekly regimen was proposed to maintain response while providing time off from pathway inhibition, which may reduce the frequency of AEs. This was the dosing frequency used for both Part 1 (now completed) and Part 2. As of MAR 2018, with approximately 28 total subjects treated with this dosing frequency in Parts 1 and 2, no DLTs had been observed, and no trends for late-onset toxicity had been noted using available nonverified data. There did not appear to be a meaningful difference between the 10 mg and 20 mg dose groups for safety or efficacy. Part 3 was initiated to compare long-term weekly dosing with long-term, low-dose daily dosing: INCB050465 20 mg QD for 8 weeks followed by 20 mg once weekly (TG20) versus INCB050465 20 mg QD for 8 weeks followed by 5 mg QD (TG5).

As of SEP 2018, the safety profile continues to be similar between dose groups. Part 4 of the study will explore and compare 2 all daily dose regimens: subjects in group TG5D will receive 5 mg QD from study start until EOT; subjects in group TG5I/M will receive 20 mg QD for the first 8 weeks and then transition to 5 mg QD. Part 4 thus directly assesses the impact of an initial higher dose on overall response in this refractory population.

### 1.8.4. Potential Risks of PI3K $\delta$ Inhibition Based on Other Agents in Class

Idelalisib was approved by the FDA in July 2014 for treatment of relapsed/refractory follicular lymphoma and relapsed small lymphocytic lymphoma and for treatment of chronic lymphocytic leukemia in combination with rituximab. Severe toxicities seen with the use of this agent include hepatotoxicity (fatal or serious occurring in 14%), fatal and/or serious diarrhea or colitis (14%), intestinal perforation, and infections including pneumonitis and cytomegalovirus (CMV) reactivation. Subjects will be monitored closely for the development of these conditions and will have treatment interrupted and dose reduced as appropriate. Subjects will receive prophylaxis for PJP and will be monitored for CMV viremia during the study.

Based on experience with idelalisib, hepatotoxicity is a risk with this class of agents. Preclinically, hepatotoxicity with INCB050465 was only seen at plasma exposures > 65-fold higher than the projected clinical exposure at 10 mg QD. The pharmacophore of INCB050465 is different from idelalisib. Other PI3K $\delta$  inhibitors with a different pharmacophore have not shown hepatotoxicity in early studies ([Savona et al 2013](#)).

### **1.8.5. Potential Risks of Ruxolitinib**

No specific findings in nonclinical repeat-dose toxicity studies identify clinical risk other than noting that consequences of immunosuppression may occur. Hypotension and increases in heart rate were noted at a high dose in a cardiovascular preclinical study. However, these findings have not been recapitulated in a clinical setting at doses up to 25 mg BID.

The primary clinical risks with ruxolitinib treatment are the potential sequelae of decreased hematopoietic proliferation attributable to the inhibition of growth factor pathways associated with JAK inhibition. Dose-dependent, reversible thrombocytopenia has been observed in studies of subjects with MF. Anemia and, less frequently, neutropenia have also been observed in studies in subjects with MF. Increased rates of infection and anemia are potential risks of myelosuppression, and there are multiple sequelae of anemia, including the burden and risks of transfusion. In healthy volunteers, rheumatoid arthritis subjects, and hormone-refractory prostate cancer subjects with greater bone marrow reserve, the effects on hematopoietic proliferation appear to be less pronounced ([ruxolitinib IB](#)).

### **1.8.6. Potential Risks of the Combination of INCB050465 and Ruxolitinib**

The principle toxicity of inhibiting both PI3K $\delta$  and JAK pathways is expected to be reversible effects on immune function. Combined inhibition may adversely affect both B-cell and T-cell immune function with resultant increased risk of a variety of infections. Subjects should be closely monitored for bacterial infections and opportunistic infections, and treatment will be interrupted for infections that can be easily managed with antibiotic therapy and discontinued for infections that are serious or require prolonged antibiotic therapy. Subjects should be monitored for varicella-zoster virus and herpes simplex virus infections and treatment started promptly. Subjects will be assessed for CMV viremia periodically during the study, and treatment started promptly if there is evidence of CMV reactivation.

Ongoing Study INCB 40093-102 combines another PI3K $\delta$  inhibitor INCB040093 with the experimental JAK1 inhibitor INCB039110 in subjects with previously treated B-cell malignancies. As of December 2015, 67 subjects have been enrolled. Five cases of PJP have been reported by subjects receiving this combination therapy (7.5% incidence); PJP is a rare but serious complication observed in lymphoma patients undergoing treatment. Because of the increased risk of PJP in subjects receiving INCB03911 in combination with INCB040093, a standard prophylaxis regimen is now required for all subjects; no additional cases of PJP have been observed. In the present study, a standard PJP prophylaxis regimen will be required for all subjects receiving combination treatment with INCB050465. Subjects who are allergic to sulfonamide antibiotics should be treated with either inhaled pentamidine or atovaquone for PJP prophylaxis. Dapsone should not be used in such subjects.

Effects on WBC, red blood cell (RBC), and platelet counts could result from JAK inhibition and result in infections, anemia, or thrombocytopenia requiring transfusions. Subjects will be

monitored closely for hematology parameters with weekly blood draws for subjects in Part 1 and twice monthly blood draws for hematology for subjects in Part 2, Part 3, and Part 4.

Combined inhibition is not expected to increase the risk of hepatic toxicity, and liver function testing will be monitored regularly. Any hepatic toxicity is expected to be reversible. These potential risks are considered acceptable in a population with MF that is at least partially refractory to ongoing ruxolitinib treatment.

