**Table 5: Guidelines for Interruption and Restarting of INCB050465**

ADVERSE EVENT	ACTION TAKEN
Chemistry	

AST and/or ALT are <math>> 5.0 \times</math> ULN.

 
Note: In subjects with bone metastasis-related elevations at baseline, contact sponsor to discuss clinical management and possible dose reductions.
	
Step 1: Interrupt study drug up to 2 weeks (14 days) until the toxicity has resolved to <math>\leq</math> Grade 1 except by approval of the medical monitor.
 
Step 2: Restart study drug at same dose. If assessed as related to study drug, restart study drug at next lower dose (or at 25% reduction, rounded down to the nearest pill strength); monitor as clinically indicated.

Hematology	

ANC <math>\leq 1.0 \times 10^9/L</math> unless because of underlying disease. Applies only if this represents a worsening grade from baseline.

Platelet count <math>\geq 50 \times 10^9/L</math> and <math>< 75 \times 10^9/L</math> unless because of underlying disease. Applies only if this represents a worsening grade from baseline.

	
Step 1: Interrupt study drug up to 2 weeks (14 days) until the toxicity has resolved to <math>\leq</math> Grade 1 or pretherapy baseline.
 
Step 2: Restart study drug at same dose and monitor as clinically indicated.

Grade 4 ANC (<math>< 0.5 \times 10^9/L</math>) regardless of baseline grade.

<math>\geq</math> Grade 3 ANC with an oral temperature of at least <math>38.5^\circ C</math> OR with <math>\geq</math> Grade 3 infection regardless of baseline grade.

Platelet count is <math>< 50 \times 10^9/L</math>, regardless of baseline grade.

	
Step 1: Interrupt study drug up to 2 weeks (14 days) until the toxicity has resolved to <math>\leq</math> Grade 1 or pretherapy baseline.
 
Step 2: Restart study drug at same dose. If assessed as related to study drug, restart study drug at next lower dose; monitor as clinically indicated.

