**Table 5: Guidelines for Interruption and Restarting of INCB050465 (Continued)**

ADVERSE EVENT	ACTION TAKEN
• Any Grade 1 or Grade 2 toxicity unless otherwise specified.	Continue study drug treatment and treat the toxicity; monitor as clinically indicated.
• Any Grade 3 toxicity, if clinically significant and not manageable by supportive care unless otherwise specified.	Step 1: Interrupt study drug up to 2 weeks (14 days) until toxicity resolves to $\leq$ Grade 1. Step 2: Restart INCB050465 at same dose. If assessed as related to INCB050465, restart at next lower dose. If interrupted for $>$ 14 days, contact the medical monitor for approval to restart INCB050465. Monitor as clinically indicated.
• Any recurrent Grade 3 toxicity after 2 dose reductions.	Discontinue study drug administration and follow-up per Protocol. (Exceptions require approval of sponsor.)
• Any other Grade 4 toxicity.	Discontinue study drug administration and follow-up per Protocol. Exceptions require approval of sponsor.

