Grade 4	Life-threatening consequences; urgent intervention indicated.

The occurrence of AEs should be sought by nondirective questioning of the subject during the screening process after signing the ICF and at each visit during the study. Adverse events may also be detected when they are volunteered by the subject during the screening process or between visits, or through physical examination, laboratory test, or other assessments. To the extent possible, each AE should be evaluated to determine:

- The severity grade (CTCAE Grade 1 to 4).
- Whether there is at least a reasonable possibility that the AE is related to the study treatment: suspected (yes) or not suspected (no).
- The start and end dates, unless unresolved at final follow-up.
- The action taken with regard to study drug.
- The event outcome (eg, not recovered/not resolved, recovered/resolved, recovering/resolving, recovered/resolved with sequelae, fatal, unknown).
- The seriousness, as per SAE definition provided in Section 8.3.1.

Unlike routine safety assessments, SAEs are monitored continuously and have special reporting requirements (see Section 8.3.2).

All AEs should be treated appropriately. If an AE is treated with a concomitant medication or nondrug therapy, this action should be recorded on Adverse Event form and the treatment should be specified on the Prior/Concomitant Medications or Procedures and Non-Drug Therapy form in the CRF.

Once an AE is detected, it should be followed until it has resolved or until it is judged to be permanent; assessment should be made at each visit (or more frequently if necessary) of any changes in severity, the suspected relationship to the study drug, the interventions required to treat the event, and the outcome.

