## **8.3. Serious Adverse Events**

### **8.3.1. Definitions**

An SAE is defined as an event that meets at least 1 of the following criteria:

- Is fatal or life-threatening.
- Requires inpatient hospitalization or prolongation of existing hospitalization, unless hospitalization is a result of:
  - A routine treatment or monitoring of the studied indication not associated with any deterioration in condition.
  - An elective surgery or preplanned treatment for a pre-existing condition that is unrelated to the indication under study and has not worsened since signing the ICF.

- A treatment on an emergency outpatient basis for an event not fulfilling any of the definitions of a SAE and not resulting in hospital admission.
- Any social reasons and respite care, in the absence of any deterioration in the subject's general condition.
- Results in persistent or significant disability, incapacity, or a substantial disruption of a person's ability to conduct normal life functions.
- Constitutes a congenital anomaly or birth defect.
- Is considered to be an important medical event or a medically significant event that may not result in death, be immediately life-threatening, or require hospitalization but may be considered serious when, based on appropriate medical judgment, the event may jeopardize the subject or may require medical or surgical intervention to prevent 1 of the outcomes listed above.

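### Protocol Sections 1.8.2 and 1.8.6 stop INCB050465 for serious infection, but Table 5 lets it restart without medical monitor approval after a serious Grade 3 infection with Grade 3 or higher neutropenia

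*Protocol*

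**What the plan says.** Two statements in the risk sections of the protocol call for a stop. Section 1.8.2, on INCB050465, says that "administration should be discontinued if there is evidence of clinically significant infection or new cancer". Section 1.8.6, on the combination, has two tiers: interruption for infections that antibiotics control readily, and a second tier in which treatment is "discontinued for infections that are serious or require prolonged antibiotic therapy".

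The dosing instructions are in Section 5.5.6, Table 5. One hematology row is triggered by ANC of Grade 3 or higher with fever, or with infection at or above the level "Grade 3 infection regardless of baseline grade". Step 1 is an interruption of up to 14 days, until recovery to Grade 1 or pretherapy baseline. Step 2 is a restart at the same dose, with this qualification: "If assessed as related to study drug, restart study drug at next lower dose; monitor as clinically indicated". The row names no approval and sets no upper limit on infection grade.

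Two general rows follow later in the table:

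- **Grade 3 toxicity** that is clinically significant and not controlled by supportive care has a similar interrupt-and-restart action. Medical monitor approval is needed only after more than 14 days, and the row excepts cases specified elsewhere.
- **"Any other Grade 4 toxicity"** leads to discontinuation, with exceptions only by sponsor approval.

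**The concern.** Section 1.8.6 sets interruption against discontinuation in a single sentence, so discontinuation there cannot mean a temporary hold. A site that follows the Table 5 row would restart drug in some subjects whom Section 1.8.6 says should stop.

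Sections 1.8.6 and 9.4.2.5 name effects on immune function, with a raised risk of infection, as the main expected toxicity of the combination. The subjects covered by this row are neutropenic as well.

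Elsewhere Table 5 is stricter. It requires medical monitor approval to restart after Grade 2 or higher diarrhea or colitis, after CMV with clinical signs, and after varicella zoster. Confirmed *Pneumocystis jirovecii* pneumonia is a permanent stop. A serious Grade 3 infection with neutropenia therefore has a looser restart control than Grade 2 diarrhea. What is at stake is subject safety and uniform conduct across sites; no endpoint or analysis is affected.

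**Working it through.** No sample size, power or error rate is involved, so the check sets the instructions side by side on worked cases.

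**Inputs**

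- Serious (Section 8.3.1): among other criteria, an event that "Requires inpatient hospitalization or prolongation of existing hospitalization" (with listed exceptions) or that "Is fatal or life-threatening".
- ANC grade (Table 7): 0.5 to below 1.0 × 10⁹/L is Grade 3. So 0.8 meets the neutropenia trigger and 1.5 does not.
- First dose reduction (Table 6): 20 mg daily to 10 mg daily; 5 mg daily to 2.5 mg daily.
- Time to recovery: assumed to be day 10 of interruption. Since 10 < 14, the rules for delays over 14 days in Sections 5.5.6, 5.5.7 and 5.6.1 are not reached.

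**Cases**

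| Case | Infection | ANC (× 10⁹/L) | Section 1.8.6 | Table 5 | Result |
|---|---|---|---|---|---|
| A | Grade 3, hospitalized | 0.8 | Discontinue | Hematology row: restart at 20 or 5 mg daily (10 or 2.5 mg daily if related), no approval | Clear conflict |
| B | Grade 4, meeting a seriousness criterion | 0.8 | Discontinue | Hematology row: same restart as A. Other-Grade-4 row, if it applies: discontinue | Ambiguous |
| C | Grade 4, meeting a seriousness criterion | 1.5 | Discontinue | Other-Grade-4 row: discontinue unless the sponsor approves an exception | No conflict |
| D | Grade 3, hospitalized, not controlled by supportive care | 1.5 | Discontinue | General Grade 3 row: restart without approval, unless its exception clause is read as deferring to Section 1.8.6 | Ambiguous |

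The count is 1 clear conflict, 2 ambiguous and 1 with none.

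**Does another provision close case A?**

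- Section 5.5.6 asks for consultation with the medical monitor when the guidelines will not be followed. A site restarting under the hematology row is following them.
- Section 5.5.7 requires a permanent stop for a related AE that the investigator or medical monitor judges to make continuation unsuitable. It does not list serious infection.
- Section 5.6.1 requires withdrawal when further participation would be injurious in the investigator's judgment. It does not list serious infection either.
- Section 8.3.2 requires SAE reporting within 24 hours, and follow-up records the action taken with study drug. That gives the sponsor notice but does not hold the restart.

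Each provision permits a stop by judgment. None requires a stop for serious infection or makes restart wait for approval.

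**The case against.** The strongest reply is that Table 5 does not override Section 1.8. Section 5.5.6 calls the table guidance and makes resumption permissive, and an investigator who reads the risk sections would stop drug. This stands to a point. A reader might infer that Table 5 compels a restart, or that no safeguard exists, and neither is so. But the two instructions still differ, and the one sites will consult for dosing is the one without the stop. Nor is Section 1.8.6 merely background, since its sentence is worded as a direction.

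A reader might also infer that Grade 4 infection with neutropenia is an equally clear conflict, because the hematology row has no upper grade limit. The documents do not settle this. That row sits under the hematology heading, while the other-Grade-4 row comes later, after the nonhematologic heading, and can be read to cover the infection itself and stop drug. The word other allows either reading.

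Nor does Grade 4 by itself make an infection serious. The description "Life-threatening consequences; urgent intervention indicated" in Section 8.1.2 belongs to a scale used only for events that CTCAE does not classify. Section 8.2 says that a Grade 3 or 4 event is not automatically an SAE. Seriousness has to be established case by case, as the hospitalization in case A does.

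Finally, Section 1.8.4, on class toxicities that include infections, speaks of interruption and dose reduction as appropriate, which is closer to Table 5. So Section 1.8 is not uniform. The choice to align Table 5 with Section 1.8.6 rests on the combination-specific wording there and on the approval steps already in Table 5.

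**Conclusion.** The point holds in a limited form. For a serious Grade 3 infection with Grade 3 or higher neutropenia that resolves within 14 days, Sections 1.8.2 and 1.8.6 stop INCB050465 and Table 5 restarts it without approval. Grade 4 infection with neutropenia and serious Grade 3 infection without neutropenia are ambiguities to be cleared up, not contradictions.

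This rests on two readings: that treatment in Section 1.8.6 includes INCB050465, which Section 1.8.2 names directly, and that discontinuation there means more than a hold. The new-cancer part of the Section 1.8.2 sentence is not contradicted in Section 5 and is not at issue.

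The number of subjects affected cannot be computed, because the documents give no infection rate for this combination. I rate it a minor to moderate safety clarification, with moderate confidence.

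**What to change.** In Table 5 and Section 5.5.7:

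1. State that an infection that is serious under Section 8.3.1, or that needs prolonged antibiotic therapy, means discontinuation of INCB050465, with any restart only by prior medical monitor approval.
2. Make the neutropenia-with-infection row and the general Grade 3 row defer to that statement.
3. State that Grade 4 infection follows the Grade 4 discontinuation row, with or without neutropenia.
4. Apply the same rule to serious CMV infection. For viremia with clinical signs, Table 5 now asks only that interruption be considered, although it already requires approval before restart.
5. Leave the confirmed *Pneumocystis* and varicella zoster rows unchanged.

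The cost is a clarification letter or a short amendment, with no new visits, procedures or subjects. A few more subjects would stop INCB050465 or need a medical monitor call before restart. SAP Section 10.2.3 records that enrollment ended early, so the change helps only subjects still on treatment.
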